## **8.3 POPULATIONS FOR ANALYSES**

All patients who undergo an EGD and gastric mapping along with confocal endoscopic microscopy.

## **8.4 STATISTICAL ANALYSES**

### **General Approach**

The fraction of patients who undergo the EGD and detailed mapping along with confocal laser microscopy and have signet ring foci identified will be reported.

#### **8.4.1 Analysis of the Primary Endpoints**

The fraction of patients who undergo the EGD and detailed mapping along with confocal endoscopic microscopy and have signet ring cell foci identified will be reported along with 80% and 95% two-sided confidence intervals.

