### **Design:**

- Phase II, single-institution study of CEM for detection of intramucosal SRC foci compared to current systematic gastric mapping procedure.

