## **1 INTRODUCTION**

### **1.1 STUDY OBJECTIVES**

#### 1.1.1 Primary Objective

- Determine if confocal endoscopic microscopy (CEM) will afford greater sensitivity for detection of SRC foci in CDH1 germline mutation carriers compared to the current method.

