## **3 STUDY IMPLEMENTATION**

### **3.1 STUDY DESIGN**

This is a Phase II single arm study designed to evaluate the efficacy of CEM to detect signet ring cell foci within the gastric mucosa of patients with hereditary diffuse gastric cancer syndrome.

At the time of endoscopy, all patients will undergo white-light, upper endoscopy with systematic gastric mapping according to our current practice pattern and as outlined by IGCLC [12] (Section 3.2.2). In addition, during this endoscopy patients will undergo CEM using the Cellvizio probe (Mauna Kea Technologies) to scan the same anatomic zones as evaluated in the systematic gastric mapping approach (Section 3.2.3). Any abnormal areas visualized with the CEM probe will be biopsied. Patients are informed of the risks of endoscopy such as gastrointestinal bleeding and perforation. The standard gastric mapping requires approximately 30 minutes of general anesthesia time. The addition of CEM adds another 30 minutes of general anesthesia but no increase in risk of general complications such as bleeding or perforation.

All biopsies are sent to Laboratory of Pathology (see Section 5.1.1). In patients co-enrolled to protocol 13C0176, leftover biopsy samples will be used for research as described in 13C0176.

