#### **3.2.2 White-light, Upper Endoscopy**

At the time of endoscopy, all patients will undergo white-light, upper endoscopy with systematic gastric mapping according to IGCLC guidelines.[8] The anatomic zones are outlined below. From each of the five zones, 6 cold forceps biopsies and photos will be obtained. The total number of biopsies will be thirty. Any visibly abnormal areas will also be biopsied.

1. Antrum
2. Transitional Zone (antrum-body)
3. Body
4. Fundus

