## **8.2 SAMPLE SIZE DETERMINATION**

Subjects who are carriers of a CDH1 mutation and participate in this trial will undergo an EGD and detailed gastric mapping along with confocal laser microscopy. Based on the historical data from NIH, 17 patients who were CDH1 mutation carriers and who underwent an EGD and detailed gastric mapping resulted in 4 with signet ring foci detected. All 4 of these patients eventually were found to have gastric cancer after undergoing a prophylactic gastrectomy. An additional 18 patients who had prophylactic gastrectomy out of 39 who had conventional random biopsies yielded 8 patients with gastric cancer.

Based on the current historical rate of 4/17 (23.5%) of mapped patients who had signet ring foci detected, it would be desirable to see if use of confocal laser microscopy could increase this detection rate substantially. With 36 patients undergoing EGD with detailed gastric mapping and confocal laser microscopy, there would be 89% power to rule out a 24% rate of signet ring detection in favor of a rate of detection consistent with 45%, with a one-sided 0.10 significance level exact binomial test. In practice, if 36 patients would undergo the procedure described and if 13/36 (36.1%) would have signet ring foci identified, then the lower one-sided 90% confidence bound on 13/36 is 25.3%, which would demonstrate statistically greater detection in the subjects tested compared to the historical fraction of 4/17 (23.5%). In addition, the upper one-sided 90% confidence bound on 13/36 is 48.2%, which demonstrates that 13/36 could be shown to be consistent with as great as a 45% detection rate.

It is expected that 18-20 patients may enroll on this study per year. Thus, to enroll 36 evaluable patients, approximately 24 months is the expected accrual period. To allow for a small number of inevaluable patients, the accrual ceiling will be set at 40 patients.

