#### **8.4.2 Analysis of the Secondary Endpoint(s)**

In those patients who choose to undergo prophylactic total gastrectomy with permanent pathologic analysis, the false negative rate, that is, the fraction of patients who have SRC foci

which were not identified by CEM, will be determined and reported along with 80% and 95% two-sided confidence intervals.

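### The primary analysis pools mapping and CEM detections and tests them against a mapping-only rate, so it cannot show that CEM is the more sensitive method

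*Combined protocol and SAP*

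**What the plan says.** The objective in 1.1.1 is to determine whether CEM "will afford greater sensitivity for detection of SRC foci in CDH1 germline mutation carriers compared to the current method". The précis and 8.1 ask the same question. The précis design statement describes a study of "CEM for detection of intramucosal SRC foci compared to current systematic gastric mapping procedure".

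Every patient receives both methods in one endoscopy. Under 3.2.2, six biopsies are taken in each of five zones: "The total number of biopsies will be thirty", plus any visible lesion. Under 3.1, "Any abnormal areas visualized with the CEM probe will be biopsied"; no number is given for these.

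The primary result in 8.4.1 is "The fraction of patients who undergo the EGD and detailed mapping along with confocal endoscopic microscopy and have signet ring cell foci identified", reported with 80% and 95% confidence intervals. Section 8.4 says the same. The test itself appears only in 8.2: a one-sided 0.10 exact binomial test of 24% against 45% with 36 patients, the 24% coming from 4/17 historical patients who had mapping alone. Section 8.2 describes the aim thus: "it would be desirable to see if use of confocal laser microscopy could increase this detection rate substantially".

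The only result specific to CEM is the secondary false negative rate in 8.4.2, for patients who choose gastrectomy. It concerns foci "which were not identified by CEM, will be determined and reported".

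**The concern.** The objective compares two methods. The analysis counts what the two find together. A patient is positive if either a mapping biopsy or a CEM-directed biopsy shows SRC, so the pooled count is never smaller than the mapping count, whatever CEM contributes. No section says which method must have made the detection, defines a CEM-only result, or plans a within-patient comparison.

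Followed exactly, the plan can meet its success rule when CEM detects no more patients than mapping, simply because the two methods find partly different patients. Given the wording of 1.1.1, that result could be reported as CEM being more sensitive. The hope in 1.2.1 that CEM may reduce the number of biopsies cannot be judged from a pooled count either.

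**Working it through.** **Inputs.** From 8.2: n = 36, null 24%, alternative 45%, one-sided 0.10, success at 13/36. From 1.2: SRC or malignancy at gastrectomy in 12/22 (55%) and 22/23 (96%). The overlap between methods is not given, so it is varied.

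**1. The plan's own figures.** With X binomial(36, p):
- P(X ≥ 13 | 0.24) = 0.070, and P(X ≥ 12 | 0.24) = 0.133, so 13 is the correct cut-off.
- P(X ≥ 13 | 0.45) = 0.893, which reproduces the stated 89%.
- The one-sided 90% bounds for 13/36 are 25.3% and 48.1% (stated: 25.3% and 48.2%).

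The calculation is sound for the pooled yield.

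**2. The same 13/36 under different attributions** (exact one-sided McNemar p for CEM over mapping):

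| Mapping positive | CEM positive | Both | p |
|---|---|---|---|
| 13 | 0 | 0 | 1.0 |
| 9 | 9 | 5 | 0.64 |
| 9 | 13 | 9 | 0.0625 |

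All three meet the success rule. Only the last favours CEM.

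**3. Chance of success when CEM has no advantage (24% each).** Let s be the share of mapping-positive patients who are also CEM-positive. Pooled yield = 0.24 + 0.24 − 0.24s.

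| s | Pooled yield | P(X ≥ 13) |
|---|---|---|
| 0 | 0.48 | 0.946 |
| 0.5 | 0.36 | 0.557 |
| 0.75 | 0.30 | 0.263 |
| 1 | 0.24 | 0.070 |

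P(X ≥ 13) equals 0.10 at a pooled yield of 0.253, that is s = (0.48 − 0.253)/0.24 ≈ 0.945. Below about 95% overlap the chance exceeds 10%.

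**4. The same, with hits independent given that SRC is present.** With prevalence q and yields m and c, pooled yield = q[1 − (1 − m/q)(1 − c/q)].
- 24% each: q = 0.55 gives 0.375 and P = 0.631; q = 0.96 gives 0.420 and P = 0.811.
- 18% each: P = 0.268 to 0.387 over the same q.
- 15% each: P = 0.116 to 0.171.
- 24% each with a lower assumed prevalence: q = 0.40 gives P = 0.436; q = 0.30 gives P = 0.213.

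**5. If CEM finds nothing.** P(X ≥ 13) depends on mapping's true yield in this trial: 7% at 24%, 26% at 30%, 51% at 35%. These yields all lie inside the exact 95% interval for 4/17 (6.8% to 49.9%).

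**6. Power for a CEM-specific answer at n = 36.** Where independence is assumed, q runs from 0.55 to 0.96.
- Exact binomial on CEM's own yield against 24%: 89% if that yield is 45%. If 45% is the pooled yield and mapping gives 24%, CEM's own yield is 37.3% (q = 0.55) or 28.0% (q = 0.96), and power is 62% or 18%.
- Exact McNemar, one-sided 0.10, 45% against 24%: 82% (q = 0.55) or 64% (q = 0.96). At n = 40 it is 86% or 69%. Reaching 89% takes about 45 or 72 patients. With near-complete overlap (23% to almost 24% positive on both), power at n = 36 is 92% to 96%.
- Exact McNemar if 45% is the pooled yield: 47% or 12%.

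**The case against.** The strongest reply is that 8.2 consistently describes an add-on design, and that its test is correctly calculated for that design. In the 95%, 56% and 26% scenarios the pooled yield really does rise above 24%, so these are not false positives for the add-on question. This is right. The figures are errors only for the claim in 1.1.1, and the mismatch could be cured by rewording the objective.

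The upper scenarios may also be too pessimistic. Section 1.2.1 describes foci as multifocal and 3.1 has CEM scan the same zones, so zero overlap is unlikely and hits may be positively correlated. Against full overlap, 1.2 puts foci at under 2% of the mucosa and often under 1 mm across. The 55% to 96% prevalence comes from gastrectomy patients, whereas eligibility also admits mutation-negative patients, so it is not a bound. Mapping here takes 30 biopsies against 88 historically (1.2), so the lower-yield scenarios may be the relevant ones. These points reduce the size of the problem without removing it.

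The secondary endpoint does not fill the gap: it covers a self-selected subset and plans no matching rate for mapping. Section 8.1 calls the comparator standard white-light endoscopy, but 3.2.2 performs the mapping under white light, so the two can be read together.

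One practical objection stands. Both methods are used in one session with no stated order, so one method's biopsies could remove a small focus or be steered by the other. Labels alone do not make the two results independent.

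**Conclusion.** The concern holds. As written, the primary analysis estimates the yield of mapping plus CEM and compares it with historical mapping. It cannot show that CEM is more sensitive than mapping.

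If both methods detect 24%, the chance of meeting the rule runs from 7% to 95% with overlap, and is 63% to 81% under independence at the assumed prevalence of 55% to 96%. It falls to 21% to 44% at an assumed prevalence of 30% to 40%. At the 55% to 96% prevalence it is 12% to 39% if each method detects only 15% to 18%. If CEM contributes nothing and mapping truly yields 24%, it is the ordinary 7% type I error. The exact size therefore rests on overlap, prevalence and yield, none of which the documents fix. The mismatch between objective and analysis rests on none of them. It should be corrected before analysis, and biopsy labels should be in place at endoscopy because they are hard to reconstruct later.

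**What to change.** - Label every biopsy at endoscopy as mapping or CEM-directed. Record the order in which the methods were used, and state in advance how a site sampled under both, or a visible lesion, is counted.
- In 8.4.1, define the CEM result as SRC in a CEM-directed biopsy and the mapping result as SRC in a mapping biopsy. Report the four-cell paired table, the exact McNemar comparison, the ratio of CEM to mapping yield, and the CEM-only added yield with its interval (for example, 8/36 would have a 95% interval of 10% to 39%).
- Report the number of biopsies and the SRC yield per biopsy for each method.
- Keep the pooled fraction, described as the yield of mapping plus CEM.
- In 8.2, say whether 45% is CEM's own yield or the pooled yield, and restate power to match.

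Alternatively, keep the pooled fraction as primary and restate the objective and the permitted conclusion, in the précis, 1.1.1 and 8.1, as the added yield of CEM on top of mapping.

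The cost is SAP wording and biopsy labels. No extra procedures are needed, and no extra patients for labelling or reporting. The drawback is power. Under independence a confirmatory paired test at 45% against 24% would need about 45 to 72 evaluable patients for 89% power, above the accrual ceiling of 40. The sponsor must either accept lower power or present the paired result as estimation.

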#### **8.4.2 Analysis of the Secondary Endpoint(s)**

In those patients who choose to undergo prophylactic total gastrectomy with permanent pathologic analysis, the false negative rate, that is, the fraction of patients who have SRC foci

which were not identified by CEM, will be determined and reported along with 80% and 95% two-sided confidence intervals.

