#### 1.1.2 Secondary Objective

- Define the false negative rate of CEM detection of SRC foci in those patients who choose to undergo prophylactic total gastrectomy with permanent pathologic analysis.

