For patients diagnosed with a pathogenic germline CDH1 mutation, a risk-reducing total gastrectomy is recommended. This is because mutation carriers are often found to have occult, early-stage (T1a) gastric cancers not visible on routine upper endoscopy. Risk-reducing total gastrectomy is recommended after the age of 20 or 5 years earlier than the age of diagnosis of the youngest affected family member. In addition, initial upper endoscopic gastric screening is recommended in all patients diagnosed with CDH1 mutation. For patients that choose not to proceed with a risk-reducing gastrectomy, annual endoscopic surveillance is currently recommended.[4, 7] Endoscopy should be done under white light with a high-definition endoscope. The International Gastric Cancer Linkage Consortium (IGCLC) recommendation is for six biopsies from each anatomical zone of the stomach (antrum, transitional zone, body, fundus, and cardia) and any visible lesion.[8] If any of the biopsies show signet ring cells on pathology then the patient is advised to undergo a therapeutic total gastrectomy.

Total gastrectomy to reduce gastric cancer risk remains a strong recommendation not only because of the lethality of invasive gastric cancer, but also because cancer screening with endoscopy is ineffective for detecting early, occult gastric cancers. In previously published series of HDGC syndrome patients, signet ring cell foci are reported to make up less than 2% of the gastric mucosa and are often less than 1 mm in diameter.[9] Gastric adenocarcinomas in HDGC syndrome patients are characterized by diffuse-type histology of signet ring cells, often with multiple foci throughout the gastric mucosa. Endoscopy rarely shows gross abnormalities or tumor masses, even though random biopsies have been known to demonstrate intramucosal foci of signet ring cells. Alternative visual enhancement with endoscopy has also been studied, including narrow band imaging, chromoendoscopy, and utilization of Congo red and indigo-carmin dyes.[10, 11] None of these enhancements has led to significantly increased rates of detection. Thus, better screening modalities are needed.

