Our group has substantial experience evaluating HDGC syndrome patients with data that support the inadequacy of current endoscopic surveillance methods. As of November 2017, we evaluated 54 patients with predisposition to gastric malignancy at the NIH. Of the 54 patients evaluated, 40 (74%) had a primary genetic abnormality predisposing to gastric malignancy with the remainder having strong family history. All patients were Caucasian, with a majority being female (66%) and a mean age of 44 years. Subjects were screened either through standard upper endoscopy (EGD) with a combination of random and targeted biopsies, or later through a systematic gastric mapping protocol developed by Yao.[12] Of the 56 EGDs performed, 17 (30%) were performed via detailed gastric mapping with resultant 88 individual biopsies in 22 distinct locations in the stomach. Of the remaining 39 (70%) standard EGDs, targeted biopsies of endoscopic abnormalities and random biopsies from the antrum and body were performed. In subjects undergoing systematic gastric mapping, signet ring cells were identified in 4 patients (24%), whereas all 39 standard EGD biopsies were absent of signet ring cells (0%). With regard to long-term follow up, in 22 patients that subsequently underwent prophylactic total gastrectomy, malignancy was identified by histology in 12 (55%) of cases. In the 4 subjects that underwent systematic gastric mapping followed by total gastrectomy, biopsies obtained during gastric mapping matched gastrectomy specimen pathology in all cases (100%). Comparatively, in the 18 subjects that underwent standard endoscopy and gastrectomy, 8 cases of malignancy were identified on gastrectomy specimen pathology (44%). See flowchart below. These preliminary results suggest that while comprehensive gastric mapping biopsies may be superior at detecting early malignancy when compared to standard EGD, the overall detection rate remains too low to recommend surveillance over prophylactic total gastrectomy with confidence.

Similarly, a retrospective study of 23 patients with a CDH1 mutation also demonstrated that EGD is not an adequate screening modality. Of the 23 patients, only 2 were found to have SRC foci on EGD with biopsy. All 23 patients underwent a prophylactic total gastrectomy. On final pathology, 22/23 patients were found to have foci of SRCs. This means that screening with EGD only had a detection rate of 9%.[\[13\]](#)

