## 5. Cardia

### 3.2.3 CEM Analysis

Patients will also undergo CEM analysis of gastric zones using the Cellvizio probe (Mauna Kea Technologies). Abnormal mucosa visualized will have images digitally captured and biopsied.

- Antrum (antegrade view): 4 quadrants (Anterior [A], Lesser curve [L], Posterior [P], Greater curve [G])
- Lower body (antegrade view): 4 quadrants [A, L, P, G]
- Middle-upper body (antegrade view): 4 quadrants [A, L, P, G]
- Fundus-cardia (retroflex view): 4 quadrants [A, L, P, G]
- Middle-upper body (retroflex view): 3 quadrants [A, L, P]
- Incisura (retroflex view): 3 quadrants [A, L, P]

Patients will receive the contrast agent fluorescein prior to endoscopy if no known allergy to fluorescein is documented. Patients who cannot receive fluorescein (e.g. pregnancy or allergy) will have CEM performed in the absence of this contrast agent.

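### CEM's false negative rate is planned only as a crude fraction of patients who elect gastrectomy; read as CEM's miss rate in all enrolled patients, it is too low if detected cases reach surgery more often than missed ones

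*Combined protocol and SAP*

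**What the plan says.** The secondary objective (section 1.1.2) is to "Define the false negative rate of CEM detection of SRC foci in those patients who choose to undergo prophylactic total gastrectomy". Section 8.4.2 carries it out: "In those patients who choose to undergo prophylactic total gastrectomy with permanent pathologic analysis, the false negative rate" is the fraction with SRC foci that CEM did not identify, given with 80% and 95% two-sided intervals. Nothing further is planned for this endpoint. Section 3.2.6 makes gastrectomy the patient's choice and asks for the tissue only if it takes place.

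The CEM result can influence that choice. Section 3.1 states: "Any abnormal areas visualized with the CEM probe will be biopsied". Section 3.2.3 says the same: "Abnormal mucosa visualized will have images digitally captured and biopsied". On biopsy results, the background in section 1.2 says: "If any of the biopsies show signet ring cells on pathology then the patient is advised to undergo a therapeutic total gastrectomy". It also recommends risk-reducing gastrectomy to pathogenic CDH1 carriers whatever the biopsy shows, and adds: "For patients that choose not to proceed with a risk-reducing gastrectomy, annual endoscopic surveillance is currently recommended".

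The labels differ between sections. Surgery after a positive biopsy is *therapeutic* in section 1.2. Section 8.2 calls the surgery in the four SRC-positive historical patients *prophylactic*, which is the word used in section 8.4.2.

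**The concern.** A CEM miss can be counted only if the patient has a gastrectomy. A CEM finding leads to a biopsy, and a positive biopsy brings specific advice for surgery. A missed case with no other positive biopsy gets only the general recommendation and may go to surveillance, in which case the miss is never seen. This is partial verification. The confidence intervals describe sampling error and do not address it.

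Section 1.1.2 describes the quantity as the false negative rate of CEM detection, and section 1.2.1 hopes for a more sensitive way to screen. A reader interested in surveillance may therefore carry the figure over to patients who keep their stomachs, the group it does not observe. The plan has no table, sensitivity analysis or stated limitation that would let that reader judge how selective surgery was.

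**Working it through.** **No planned figure to reproduce.** The documents give no expected value, precision or number of gastrectomies for this endpoint. The historical counts agree between sections 1.2 and 8.2: 4 + 18 = 22 gastrectomies and 4 + 8 = 12 malignancies (12/22 = 55%).

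**Direction.** Let f be the true miss rate among patients with SRC, gd the probability of gastrectomy when CEM found the SRC, and gm that probability when CEM missed it. Then

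expected crude rate = f·gm / (f·gm + (1 − f)·gd).

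For f strictly between 0 and 1 this is below f when gm < gd, equal to f when gm = gd, and above f when gm > gd.

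**What the history says about gd and gm.**
- After positive mapping: 4/4 operated on (section 8.2). The exact 95% interval is 40-100%.
- After negative standard EGD: 18/39 = 46% (section 8.2).
- After negative mapping: section 1.2 counts only four mapped patients with surgery ("In the 4 subjects that underwent systematic gastric mapping followed by total gastrectomy"). Section 8.2 says these were the four with foci, so by deduction 0 of 17 − 4 = 13. Pooled with standard EGD: 18/52 = 35%.

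The 17 and 39 are counts of EGDs (56 in 54 patients), mapping came later than standard EGD, and all of this concerns biopsy rather than CEM.

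**Size, as an illustration.** Assumed: 20 patients with SRC (close to 36 × 12/22 = 19.6), f = 35%, so 13 found and 7 missed; all 13 found cases operated on; k of the 7 misses found by the concurrent mapping and operated on; the other 7 − k operated on with probability v. Then

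expected crude rate = (k + (7 − k)v) / (k + (7 − k)v + 13).

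Three values of v are used: 18/52, 18/39 and a higher one, 18/23 = 78%. The 23 is 40 − 17, from "Of the 54 patients evaluated, 40 (74%) had a primary genetic abnormality predisposing to gastric malignancy with the remainder having strong family history" less the 17 mapped, and assumes that all 18 operated standard-EGD patients were among those 23. Example: k = 0, v = 18/39 gives 3.23/16.23 = 19.9%.

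| k | v = 35% | v = 46% | v = 78% | 95% interval covers 35% | 80% interval covers 35% |
|---|---|---|---|---|---|
| 0 | 16% | 20% | 30% | 73, 83, 95% | 46, 61, 84% |
| 2 | 22% | 25% | 31% | 94, 95, 97% | 73, 80, 88% |
| 4 | 28% | 29% | 33% | 99, 99, 98% | 95, 95, 92% |

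Coverage is exact, with misses binomial (20, 0.35), and uses Clopper-Pearson intervals because the plan names no method. With full verification it is 97% and 90%. The k = 2 and k = 4 rows treat that many misses as always verified. If instead each miss has a 2/7 chance of being mapping-positive, the 95% interval covers 87, 91 and 96%.

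**Sensitivity to gd.** Take k = 4 and v = 18/23, and let all biopsy-positive cases (the 13 and the 4) be operated on with probability g. Expected rates are 33.7% at g = 0.90, 34.8% at 0.80 and 35.4% at 0.75: (3 + 2.35)/(3 + 2.35 + 9.75). The sign has reversed at 0.75.

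**Worked example of the proposed analysis.** Assume 36 patients: 13 CEM-positive, all operated on with SRC; 23 CEM-negative, 8 operated on, 2 with SRC.
- Crude: 2/15 = 13% (95% interval 2-40%).
- Prevalence in the 15 unverified equal to the verified (2/8 = 25%): (2 + 3.75)/(15 + 3.75) = 31%.
- Half (12.5%): 3.875/16.875 = 23%. Twice (50%): 9.5/22.5 = 42%.
- Sampling error in 2/8 alone (3.2-65.1%), applied to all 23 CEM-negatives as 23p/(13 + 23p): 5-54%.

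**The case against.** The plan estimates what it says it estimates. Sections 1.1.2, 8.1 and 8.4.2 all restrict the rate to patients who choose gastrectomy, and no test or decision depends on it. That stands and lowers the severity: the fault appears only when the restriction is dropped.

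Section 1.2 recommends gastrectomy to every pathogenic CDH1 carrier, which narrows the gap between found and missed cases. Every patient also has 30 mapping biopsies (section 3.2.2), so some CEM misses will be biopsy-positive anyway. Both points stand. Against the first, past uptake after a negative standard EGD was incomplete, and section 2.1.1 also admits patients without a CDH1 mutation, whom that recommendation does not mention.

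The adjusted figure is imprecise (5-54% in the example), the crude 95% interval there already contains the adjusted 31%, and the equal-prevalence case assumes that surgery is unrelated to SRC given the test results, which mutation status could break. This stands, and is why the adjustment is proposed only as exploratory.

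A reader might infer from the history that 18/23 caps the surgery rate in missed cases and so guarantees a minimum understatement. It does not. It concerns biopsy-negative patients with or without SRC, and the SRC status of those not operated on is unknown. Verification of missed cases could be anything up to 100%.

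**Conclusion.** The point holds conditionally. The crude fraction is a valid description of operated patients. As CEM's miss rate in all enrolled patients it is too low if found cases reach surgery more often than missed ones. The documents make that plausible, and the plan contains nothing that would reveal it.

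A reader might go further and conclude that the reported rate will understate CEM's misses by a known amount. The documents do not support this: the counts are small and indirect, and the bias can be zero or reversed. The illustrated rates against an assumed true 35% (16-30%, 22-31% and 28-33% as mapping finds 0, 2 or 4 of the 7 misses) depend on every found case being operated on. Under those assumptions, poor coverage of the 95% interval arises mainly when mapping finds none of CEM's misses.

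A reader might also take the word *prophylactic* in section 8.4.2 to exclude patients operated on after a positive biopsy, which would drive the rate towards 100%. Sections 8.2 and 3.2.6 point to including them, so this is wording to reconcile and not a planned exclusion. Overall this is a cheap improvement of minor to moderate weight.

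**What to change.** 1. In section 8.4.2, define the set as all patients with total gastrectomy for any reason, and the rate as patients with SRC on the specimen not identified by CEM, divided by all patients with SRC on the specimen. Reconcile the *therapeutic* label (section 1.2) with *prophylactic* (sections 8.2 and 8.4.2).
2. Keep the crude rate and its intervals, labelled as applying to operated patients.
3. Add a table of gastrectomy (yes/no) by CEM result and mapping result, and report the SRC fraction among CEM-negative patients who were operated on.
4. As an exploratory sensitivity analysis only, show the rate for all enrolled patients over a range of assumed SRC prevalence in unverified CEM-negatives, for example half, equal to and twice that in verified ones. The equal case is the Begg-Greenes estimate. State its assumption, and that it is not estimable if no CEM-negative patient is operated on.

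Cost: SAP wording, one table and one short analysis, with no new procedures or patients. The data are largely collected already; sections 3.1 and 6.1 do not say that each biopsy is recorded as CEM-directed or mapping, so that should be confirmed. The downside is that the adjusted figure will be imprecise and may look less favourable than the crude one.
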